4.2. Part 2 – Rifampin (CYP3A4 Inducer)

In Part 2, Period 1, a single oral dose of 200 mg LOXO-305 will be administered on Day 1, following a fast of at least 10 hours prior to and 4 hours after dosing with LOXO-305. Blood samples for PK analysis of LOXO-305 in the absence of rifampin will be taken up to 168 hours postdose of LOXO-305 on Day 1.

In Part 2, Period 2, multiple oral doses of 600 mg rifampin will be administered QD from Day 8 until Day 23 inclusive (for a total of 16 consecutive days) and co-administered with a single oral dose of 200 mg LOXO-305 on Days 8 and 17. On Days 8 and 17, a single oral dose of 200 mg LOXO-305 and a single oral dose of 600 mg rifampin will be co-administered in the morning following a fast of at least 10 hours prior to and 4 hours after

dosing with LOXO-305 and rifampin. On Days 9 to 16 and Days 18 to 23, the dose of rifampin will be administered alone at the actual time of the Day 1 LOXO-305 dose (\pm 1 hour), following a fast of at least 8 hours prior to and 2 hours after dosing with rifampin. Blood samples for PK analysis of LOXO-305 in the presence of rifampin will be taken up to 24 hours postdose of LOXO-305 on Day 8 and up to 168 hours postdose of LOXO-305 on Day 17.

Urine samples will be collected on Days 8, 11, 15, and 17 of Part 2 only (and stored for future potential assessment of 6β -hydroxycortisol and free cortisol concentrations to evaluate the level of CYP3A enzyme induction and/or for further exploratory analysis).

There will be a washout period of 7 days between the dose of LOXO-305 on Day 1 (Period 1) and the first dose of rifampin and dose of LOXO-305 on Day 8 (Period 2).

To assess their eligibility to enter the study, potential subjects will be screened within 28 days (Days -29 to -2) and be admitted to the CRU on Day -1 (Check-in). Replacement subjects may be enrolled only if deemed necessary by the Sponsor.

Subjects will be confined at the CRU from the time of Check-in (Day -1) until EOT on Day 24 upon completion of all PK and safety assessments or ET if the subject discontinues. A follow-up phone call will occur for all subjects who received at least 1 dose of study drug (including subjects who are terminated early) 7 days (± 2 days) after EOT or ET.

Replacement subjects may be enrolled only if deemed necessary by the Sponsor.

4.3 Overall

The start of the study is defined as the date the first subject who is enrolled in the study signs an Informed Consent Form (ICF). Note that enrolled subjects are defined as those subjects who are assigned a dose of study drug; this definition excludes screen failure subjects.

In this study, physical examinations, 12-lead ECGs, vital signs, How Do You Feel? inquiries, clinical chemistry panel, coagulation parameters, creatine kinase, complete blood count, urinalysis and recording of concomitant medications will be performed at specified times during the study. The AEs and serious adverse events (SAEs) will be collected beginning at informed consent. The AEs will be reported throughout the study (ie, from signing of the ICF until End of Study [EOS], or until ET if the subject discontinues from the study and does not complete a follow-up phone call), either as subject medical history (if the event is reported as beginning prior to signing of the ICF or if the event occurs prior to study drug administration on Day 1 and is assessed as not related to study procedures by the Investigator [or designee]) or as AEs (if the event occurs after signing of the ICF but prior to study drug administration on Day 1 and is assessed as related to study procedures by the Investigator [or designee], or if the event occurs after study drug administration on Day 1 through EOT or ET regardless of relationship to study drug). From EOT or ET through EOS, only AEs assessed as related to study drug by the Investigator (or designee) are to be reported. All SAEs that develop from the time of ICF signing until EOS (or ET, if the subject discontinues from the study and does not complete a follow-up phone call) are to be reported. Study completion is defined as the time of the last subject's follow-up phone call.

5. SAMPLE SIZE JUSTIFICATION

Twenty-four healthy adult male and female subjects (women of non-childbearing potential only); 12 subjects in Part 1 and 12 subjects in Part 2 to ensure that 20 subjects complete the study. This is a phase 1 study and the sample size is not based upon any formal power calculations but is consistent with previous studies of a similar design.

Each subject will participate in either Part 1 or Part 2, but not both. Part 1 will be divided into 2 cohorts; a sentinel cohort will comprise 3 subjects and the second cohort will comprise 9 subjects, for a total of 12 subjects.

Every attempt will be made to enroll at least 3 subjects of each sex in the study.

6. STUDY TREATMENTS

The study treatment sequence names and ordering to be used in the TFLs are presented in Table 1.

Table 1:	Presentation of Stud	y Treatment Seq	uences in TFLs
----------	----------------------	-----------------	----------------

Part	Study Treatment Sequence	Order in TFLs
1	LOXO-305 alone/LOXO-305 and itraconazole	1
2	LOXO-305 alone/LOXO-305 and rifampin once /LOXO-305 and rifampin QD	2

The study treatment names, and ordering to be used in the TFLs are presented in Table 2,

Table 3. Presentation of Study Treatments in TFLs – Part 1 Non AE and PK Outputs

Study Treatment	Order in TFLs
200 mg LOXO-305 Alone	1
200 mg LOXO-305 + 200 mg itraconazole QD	2

Table 4 and Table 4.

Table 2: Presentation of Study Treatments in TFLs – Part 1 AE Outputs

Study Treatment	Order in TFLs
200 mg LOXO-305 Alone	1
200 mg itraconazole Alone	2
200 mg LOXO-305 + 200 mg itraconazole QD	3

Table 3.Presentation of Study Treatments in TFLs – Part 1 Non AE and PKOutputs

Study Treatment	Order in TFLs
200 mg LOXO-305 Alone	1
200 mg LOXO-305 + 200 mg itraconazole QD	2

Table 4:Presentation of Study Treatments in TFLs – Part 2

Study Treatment	Order in TFLs
200 mg LOXO-305 Alone	1
200 mg LOXO-305 + 600 mg rifampin once	2
200 mg LOXO-305 + 600 mg rifampin QD	3

All treatments described above are the planned treatments. The TFLs will reflect the actual treatments received.

7. DEFINITIONS OF POPULATIONS

Any protocol deviations will be considered prior to database lock for their importance and taken into consideration when assigning subjects to populations.

7.1. All Subjects Population

The all subjects population will include all subjects who signed the ICF and had any study assessment recorded in the database per the protocol.

7.2. Safety Population

The safety population will include all subjects who received at least 1 dose of study treatment (LOXO-305). Subjects will be classified into groups based on actual treatment received.

7.3. Pharmacokinetic Population

The PK population will include all subjects who received at least 1 dose of LOXO-305, have at least 1 quantifiable PK concentration, and for whom at least 1 PK parameter can be computed. A subject may be excluded from the PK summary statistics and statistical analysis if the subject has an AE of vomiting that occurs at or before 2 times the median t_{max} .

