1.4.2. Pharmacokinetics

As of 25 October 2019, preliminary steady-state PK data (Day 8 of Cycle 1) were available from 25 patients enrolled in LOXO-BTK-18001. These data demonstrate that LOXO-305 is absorbed after oral administration with a median time to maximum observed concentration (t_{max}) of approximately 2 hours and low clearance (Table 1).

Although the plasma half-life could not be calculated with certainty because of the limited sampling interval (0 to 8 hours), it appears to be approximately 18 hours. Steady-state PK parameters of LOXO-305 in these cancer patients are presented in Table 1. Following administration of the 100 mg QD, 150 mg QD, or 200 mg QD, mean unbound trough plasma levels of LOXO-305 exceeded the concentration required for 90% inhibition (IC₉₀) of the C481S mutant of BTK in vitro.

 Table 1: Preliminary Pharmacokinetic Parameters of LOXO-305 in Patients with Cancer (Study LOXO-BTK-18001)

Dose (mg)	Ν	C _{max} (ng/mL)	t _{max} (h)	AUC ₀₋₂₄ (ng·h/mL)	CL/F (L/h)	t _½ (h)
25 mg (QD)						
50 mg (QD)						
100 mg (QD)						
150 mg (QD)						
200 mg (QD)						

Abbreviations: AUC₀₋₂₄ = area under the concentration-time curve from Hour 0 to 24 hours postdose; CL/F = apparent oral clearance; C_{max} = maximum observed plasma concentration, CV = coefficient of variation; N = number of patients; QD = once daily; $t_{1/2}$ = apparent terminal elimination half-life; t_{max} = time to maximum observed concentration. Mean (CV%) data are presented for C_{max} , AUC₀₋₂₄, CL/F, and $t_{1/2}$; median (minimum-maximum) data are presented for t_{max} . Data cutoff date: 25 October 2019.

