8.5.1.4. Anomalous Values

If a value is considered to be anomalous due to being inconsistent with the expected PK profile, it may be appropriate to exclude this point from the PK analysis. However, the exclusion of data must have strong justification and will be documented in the raw data and the CSR.

Embedded BLQ values may be considered anomalous depending on the route of administration and the characteristics of the drug.

Subjects with positive predose values greater than 5% of Cmax may be excluded from the summary statistics and statistical analysis at the discretion of the Pharmacokineticist.

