8.5.3.1. Statistical Analyses

A statistical analysis will be conducted to investigate the drug-drug interaction on the PK of LOXO-305 for AUC₀₋₂₄, AUC_{0-t}, AUC_{0-inf}, and C_{max} . The comparisons of interest are:

Study Part 1:

To access the impact of multiple oral doses of itraconazole on the single oral dose PK of LOXO-305 (AUC_{0-t}, AUC_{0-inf}, and C_{max})

• 200 mg itraconazole co-administered with 200 mg LOXO-305 (test treatment) vs 200 mg LOXO-305 alone (reference treatment).

Study Part 2:

To assess the effect of multiple oral doses of rifampin (strong CYP3A4 inducer) on the single oral dose PK of LOXO-305 (AUC_{0-t}, AUC_{0-inf}, and C_{max}) in healthy adult subjects

• 600 mg rifampin QD co-administered with 200 mg LOXO-305 (test treatment, Day 17) vs 200 mg LOXO-305 alone (reference treatment)

To assess the effect of a single oral dose of rifampin on the single oral dose PK of LOXO-305 (AUC₀₋₂₄, and C_{max})

• 600 mg rifampin once co-administered with 200 mg LOXO-305 (test treatment, Day 8) vs 200 mg LOXO-305 alone (reference treatment)

The ln-transformed³ PK parameters (AUC₀₋₂₄, AUC_{0-t}, AUC_{0-inf}, and C_{max}) will be analyzed using a mixed model.⁴ The model will include actual treatment as fixed effect, and subject as a random effect.

For each PK parameter separately, the least squares mean (LSM) for each treatment, difference in LSMs between the test and reference treatments, and corresponding 90% confidence interval (CI) will be calculated; these values will then be exponentiated to give the geometric least squares mean (GLSM), geometric mean ratios (GMR), and corresponding 90% CI.

Additionally, the pooled estimate (across all treatments) of the within-subject CV will be calculated, and residual plots will be produced to assess the adequacy of the model(s) fitted.

Examples of the SAS code that will be used are as follows:

Mixed Model Analysis

```
proc mixed data = <data in>;
by parcatln parcatl paramn param;
class trtan usubjid;
model lpk = trtan / cl residual ddfm = kr;
lsmeans trtan / cl pdiff = control('1') alpha = 0.1;
random intercept / subject = usubjid;
```

```
ods output lsmeans = <data out>;
  ods output diffs = <data out>;
  ods output covparms = <data out>;
run;
```

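### The vomiting rule is optional and drops the whole subject, so in Part 2 vomiting after the Day 8 or Day 17 dose can remove an intact pair; elsewhere the gap is an unguided keep-or-drop choice

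*SAP*

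**What the plan says.** SAP 7.3 defines the PK population and then adds: "A subject may be excluded from the PK summary statistics and statistical analysis if the subject has an AE of vomiting", limited to vomiting "that occurs at or before 2 times the median" tmax. Protocol 8.2.1 carries the same rule. Neither names a profile, day or period, the dose from which the window runs, which treatment's median applies, who decides, when, or any sensitivity analysis.

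SAP 8.5.1.4 has a second rule of the same kind: "Subjects with positive predose values greater than 5% of Cmax may be excluded from the summary statistics and statistical analysis", at the pharmacokineticist's discretion.

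The analysis the rule feeds is in SAP 8.5.3.1: "The model will include actual treatment as fixed effect, and subject as a random effect". The 90% level is set by "lsmeans trtan / cl pdiff = control('1') alpha = 0.1". Part 1 has one comparison (Day 12 vs Day 1). Part 2 has two: Day 17 vs Day 1 for AUC0-t, AUC0-inf and Cmax, and Day 8 vs Day 1 for AUC0-24 and Cmax. All three serve primary objectives.

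On numbers, SAP section 5 gives "12 subjects in Part 1 and 12 subjects in Part 2 to ensure that 20 subjects complete the study" and says that "the sample size is not based upon any formal power calculations".

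**The concern.** Vomiting soon after a dose makes that dose's profile doubtful. It says nothing against the same subject's profiles from other days. A rule whose unit is the subject discards those too, and Part 2 has only 12 subjects.

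The permissive wording adds a second problem. Two teams following the SAP could reach different primary ratios from the same data, one keeping the subject and one not, and both would comply.

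The missing details matter in practice. Subjects also take itraconazole or rifampin alone on many days, so vomiting has to be tied to a particular LOXO-305 dose. If the median tmax is the study's own, it is known only once concentrations are available, because SAP 8.5.1 reads tmax from the concentration profiles. At stake are the precision of two primary comparisons in Part 2 and the reproducibility of the ratio in both parts.

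**Working it through.** **The plan's own figure.** 12 + 12 = 24 enrolled for 20 completers, an implied loss of 4/24 = 1/6. No power or precision figure is stated, so there is nothing further to reproduce.

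**Window.** Protocol 1.4.2 gives a median tmax in patients "of approximately 2 hours and low clearance". If that value applied, the window would be 2 × 2 h = 4 h.

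**Step 1: which pairs are lost if the subject is dropped.**

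| Vomiting after | Pair already affected | Intact pair also removed |
|---|---|---|
| Part 1, Day 1 or Day 12 | Day 12 vs Day 1 | none (only one pair exists) |
| Part 2, Day 1 | both (each uses Day 1) | none |
| Part 2, Day 8 | Day 8 vs Day 1 | Day 17 vs Day 1 |
| Part 2, Day 17 | Day 17 vs Day 1 | Day 8 vs Day 1 |

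Needless pair loss therefore arises on 2 of the 5 LOXO-305 dosing occasions, both in Part 2.

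**Step 2: precision cost of one lost pair.** The half-width of the 90% CI on the log scale is t(0.95, df) × s_w × √(2/n). The within-subject SD s_w cancels in the ratio of n = 11 to n = 12.

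- Two treatments in the model (AUC0-24: Days 1 and 8), df = n − 1: t(0.95, 10)/t(0.95, 11) × √(12/11) = 1.009 × 1.044 = 1.054, so +5.4%.
- Three treatments (Cmax), df = 2(n − 1): t(0.95, 20)/t(0.95, 22) × √(12/11) = 1.004 × 1.044 = 1.049, so +4.9%.

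AUC0-t and AUC0-inf take one value or the other, depending on whether Day 8 values enter their models.

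For absolute size, a within-subject CV must be assumed because the documents give none. With three treatments, going from 12 to 11 subjects moves the CI factor from 1.149 to 1.157 at CV 20%, and from 1.228 to 1.241 at CV 30%.

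**Step 3: what profile-level exclusion saves.** These are standard errors of the log-ratio from generalised least squares with a random subject effect, assuming within-subject CV 20% and between-subject CV 30%.

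| Case | Profile dropped | Subject dropped |
|---|---|---|
| Part 2, Day 8 vomiting: Day 17 vs Day 1 | 0.0809 | 0.0844 (+4.4%) |
| Part 2, Day 8 vomiting: Day 8 vs Day 1 | 0.0834 | 0.0844 |
| Part 1 | 0.0839 | 0.0844 (0.7% apart) |

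The first entry, 0.0809, equals the full-data value, so nothing is lost for the unaffected comparison.

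**Step 4: shift if the affected profile is kept.** With 12 complete pairs the log-ratio is the mean paired difference. One profile that loses a fraction L of its exposure multiplies the geometric mean ratio by (1 − L)^(1/12) if it is the test dose, or (1 − L)^(−1/12) if it is the reference dose. The values of L are assumptions.

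| Exposure lost | Test dose | Reference dose |
|---|---|---|
| 25% | 0.976 | 1.024 |
| 50% | 0.944 | 1.059 |
| 75% | 0.891 | 1.122 |

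**The case against.** The best defence is that a sensible team would apply the rule by profile and that the optional wording lets it keep a profile when little drug was lost. The second half has force: some vomiting inside a window of about 4 h may cost little exposure. The first half is not what the text says. Where the SAP means a profile it says so: in SAP 8.5.1.1 a wholly unquantifiable profile is dropped, as a profile and without discretion. SAP 8.5.1.3 likewise fixes exclusion of AUC0-inf above 30% extrapolation, value by value.

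Other safeguards exist but do not reach this case. The opening of SAP section 7 concerns protocol deviations before lock. The strong-justification requirement in SAP 8.5.1.4 concerns anomalous values. SAP 8.5.3 makes exclusions visible in the tables but does not guide them.

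The size is also open to challenge, and this stands. The precision cost is small, no vomiting rate is given, and the plan sets no equivalence limits that a shift could overturn. SAP 8.1 itself urges caution in interpretation. Keeping the profile does not necessarily spoil coverage either, because the outlier widens the interval as well. In a simulation of 12 pairs with a true ratio of 1 and CV 20%, coverage of the 90% CI was 0.905 at 50% loss and 0.934 at 75% loss, while the mean CI factor rose from 1.152 with no loss to 1.191 and 1.284. The harm is a shifted estimate and a wider interval.

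Three stronger readings are tempting, and the documents do not support them:

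- A reader might infer that any vomited dose costs valid pairs. Step 1 shows that it does not in Part 1 or for Part 2 Day 1.
- A reader might infer that staff will choose with results in view. No decision-maker is named for vomiting, nothing says who sees concentrations beforehand, and open-label describes treatment, not assay results.
- A reader might infer that the ratio moves only downward. A vomited reference dose moves it up.

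**Conclusion.** The point holds in a limited form. As written, the rule can remove one intact pair per PK parameter in Part 2, after Day 8 or Day 17 vomiting. This costs about 5.4% (AUC0-24) or 4.9% (Cmax) in CI width on the log scale, figures that need no assumed CV. In Part 1 and for Part 2 Day 1 vomiting, the defect is only the unguided choice. Across both parts that choice matters more than the lost precision: at an assumed 50% exposure loss in one profile of 12, keeping it moves the ratio by a factor of 0.944 or 1.059.

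The predose rule shares the subject-level wording but is less likely to be triggered. Seven days is 168/18 ≈ 9.3 half-lives at the approximate 18 h in protocol 1.4.2, a value the protocol itself calls uncertain.

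This is a modest but real weakness, worth correcting before database lock.

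**What to change.** Replace the vomiting sentence in SAP 7.3 with: *A LOXO-305 profile will be left out of the PK summaries and the statistical analysis if vomiting occurs within twice the median tmax for that treatment, timed from that LOXO-305 dose; the subject's other profiles are retained.* Then:

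- Apply the rule mechanically from AE and dose times, and document the outcome before the treatment comparisons are run. The decision cannot be required before concentrations are seen, because a treatment's observed median tmax depends on them. The protection comes from leaving no discretion.
- Report a sensitivity analysis with the affected profiles included.
- In SAP 8.5.1.4, change only the unit of the predose rule from subject to profile.
- Record the difference from protocol 8.2.1 in SAP section 10. SAP section 1 says the SAP supersedes the protocol's statistical text, so no protocol amendment is needed for this.

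The random-subject model in SAP 8.5.3.1 already accepts a subject with a missing profile, so the model needs no change. The cost is a SAP revision and one extra analysis. The downside is that an occasional profile with little drug loss will be dropped, and some discretion is given up; the sensitivity analysis shows what that does to the ratio.

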8. STATISTICAL METHODOLOGY

8.1. General

Listings will be provided for all data captured in the database. Listings will include all subjects assigned to the all subjects population and include data up to the point of study completion or discontinuation. Subjects are generally considered to have completed the study

if they completed all protocol-specified procedures and assessments for the end-of-treatment visit. Any subject who discontinued the study will be identified accordingly in the listings. Summaries and statistical analyses will include the subjects assigned to the relevant population based on data type.

Data analysis will be performed using the SAS[®] statistical software package Version 9.4 (or higher if upversioned during the study).

Analysis Data Model (ADaM) datasets will be prepared using Clinical Data Interchange Standards Consortium (CDISC) ADaM Version 2.1 (or higher if upversioned during the study) and CDISC ADaM Implementation Guide Version 1.2 (or higher if upversioned during the study). Pinnacle 21 Community Validator Version 2.2.0 (or higher if upversioned during the study) will be utilized to ensure compliance with CDISC standards.

Caution should be used when interpreting results from the statistical analyses conducted in this study because the sample size is not based on power calculations.

Where reference is made to 'all calculations', this includes, but is not limited to, summary statistics, statistical analyses, baseline derivation, and changes from baseline.

8.1.1. Calculation of the Summary Statistics

For continuous data the following rules will be applied:

- Missing values will not be imputed, unless specifically stated otherwise.
- Unrounded data will be used in the calculation of summary statistics.
- If the number of subjects with valid observations (n) <3, summary statistics will not be calculated, with the exception of n, minimum, and maximum.
- As ET data is not associated with any scheduled timepoint, it will be excluded from all calculations of summary statistics.
- Post dose repeats and unscheduled assessments will not be included in calculation of summary statistics.

For categorical data the following rules will be applied:

- If the categories of a parameter are ordered (eg, AE severity), all categories between the possible minimum and maximum categories will be included, even if n = 0 for a given category. If the categories are not ordered (eg, race), only those categories for which there is at least 1 subject represented will be included.
- Missing values will not be imputed, with the exception of AEs where the 'worst-case' approach will be taken (see Section 8.6.1), or unless specifically stated otherwise. A 'missing' category will be included for any parameter for which information is missing. This will ensure that the population size totals are consistent across different parameters.

8.1.2. Repeat and Unscheduled Readings

For vital signs and ECG data only, any predose value recorded in addition to the original value or a postdose value recorded within 15 minutes of the original value will be defined as a repeat value; any postdose value recorded more than 15 minutes after the original value will be defined as an unscheduled value. For all other data types (eg, laboratory parameters), any value recorded in addition to the original value will be defined as an unscheduled value.

The original scheduled value will be used in all calculations post dose. In the event of any repeats or unscheduled measurements taken pre-dose the values will be considered when determining the baseline value for each period.

Post dose repeats, unscheduled assessments, and ET measurements will be excluded from all calculations, with the exception of the baseline derivation (see Section 8.1.3).

